2.3 STUDY ENDPOINTS

2.3.1 Primary Efficacy Endpoint

The primary efficacy endpoint is the overall survival (OS), as measured from the time of randomization until death from any cause.

2.3.2 Secondary Efficacy Endpoints

Secondary efficacy endpoints are:

- Morphologic Complete Remission (CR) rate
- Transfusion independence
- Complete Remission without Minimal Residual Disease (CR_{MRD}) rate
- Cytogenetic Complete Remission (CRc) rate

2.3.3 Exploratory Endpoints

Exploratory endpoints are:

- Composite Complete Remission (cCR) rate
- Relapse Free Survival (RFS)
- Progression Free Survival (PFS)
- Duration of Morphologic Complete Remission (CR)
- Duration of Composite Complete Remission (cCR)
- Time to CR
- Morphologic CR within 6 cycles rate
- Quality of Life

2.3.4 PK Endpoints

PK endpoints are:

- To characterize the pharmacokinetics (PK) of pracinostat and its main metabolites in AML patients by a population pharmacokinetic approach
- To characterize demographic, physiopathological and therapeutic covariates that may influence pracinostat PK parameters and their interindividual variability

- To characterize the pracinostat exposure-response relationship for safety and efficacy endpoints (PK/PD)
- To assess the possible drug interaction of pracinostat on the PK of AZA in AML patients by comparing the descriptive statistics of PK parameters of azacitidine in the two groups

3 STUDY DESIGN

3.1 OVERALL STUDY DESIGN

This is a phase III, multicenter, double-blind, randomized study of pracinostat vs. placebo with azacitidine (AZA) as background therapy in patients ≥ 18 years of age with newly diagnosed acute myeloid leukemia (AML), excluding acute promyelocytic leukemia and cytogenetic favorable-risk AML, who are unfit to receive intensive remission induction chemotherapy due to age ≥ 75 years or comorbidities.

Patients will be randomized in a 1:1 ratio to one of two groups: Group A (experimental group) to receive pracinostat plus AZA and Group B (control group) to receive placebo plus AZA. Randomization will be stratified by cytogenetic risk category (intermediate vs. unfavorable-risk, according to SWOG Cytogenetic Risk Category Definitions, Appendix B of the protocol) and ECOG performance status (0-1 vs. 2, Appendix C of the protocol). Treatments will be administered based on 28-day cycles, with pracinostat/placebo administered orally once every other day, 3 times a week for 3 weeks, followed by one week of no treatment and AZA administered for 7 days of each cycle.

Study treatment, defined as the treatment with pracinostat/placebo (study drug) in addition to the background therapy (AZA), should continue until there is documented disease progression, relapse from complete remission (CR), or non-manageable toxicity. A minimum of 6 cycles may be required to achieve a complete remission.

Once permanently discontinued from study treatment, patients will enter the Long-term Follow-up phase (also called ‘in-study long-term follow-up’) of the study and will be followed for assessment of disease progression, if applicable, and survival every 3 months (± 1 month) until death.

The end of this study is defined when 390 events (deaths) have occurred. Patients who are receiving study treatment at the end of the study may have the opportunity to continue to receive the study drug to which they were randomized to (Post-Study Observation Period), until the Sponsor informs the Investigators of the appropriate course of action based on the study results.

The Post-Study Observation Period is defined as the period starting from the end of the study for a maximum of 24 months.

An interim analysis at 67% (2/3) of information (260 over 390 events (deaths), being the study event-driven) will be performed for both futility (non-binding) and superiority.

3.2 SCHEDULE OF ASSESSMENTS

Assessments	Screening ^A		Study Treatment Cycles (28 days) ^B											End of Treatment Visit	In-study Long-Term Follow-Up ^V
	Day -28 to -1	Day -8 to -1	Day1	Day2	Day3	Day4	Day5	Day6	Day7	Day8	Day9	Day15	Day 21-26		
Obtain Informed Consent ^C	X														
Randomization via IWRS			[X] ^D C1 Only												
Medical history, demographics	X		[X] ^D Only C1												
Bone Marrow aspirate/biopsy and classic cytogenetic testing ^E	X												X even cycles		
Smoking status ^F	X														
Vital signs ^G	X		X									[X]	X Only C2	X	
Physical examination ^H	X		X												
ECOG Performance Status ^I	X		X											X	
Transfusion of RBC or platelets ^J			X										X even Cycles		
Quality of Life Questionnaire ^K			X odd cycles											X	
12 Lead ECG ^L	X		X	X	X							[X]	X		

CBC, Serum Chemistry, coagulation, serum pregnancy test ^M		X	X C2 only									[X] C1 only	X	X	
HIV, HBV and HCV serology ^N		X													
Urine dipstick pregnancy test ^O			[X]												
Pracinostat Pop PK Sampling ^P			[X]	[X]	[X]							[X]			
Pracinostat/ placebo Administration ^Q	3 times a week/x3 weeks														
			X		X		X			X		X			
Azacitidine Administration (Days 1-7) ^R			X	X	X	X	X	X	X						
Azacitidine Administration (Days 5-2-2) ^S			X	X	X	X	X			X	X				
Study Drug accountability/dispensation ^T			X									[X] compliance		X	
Adverse events/toxicity assessment ^U	X		X	X	X	X	X	X	X	X	X	[X]	X	X	
Concomitant medication review ^U	X		X	X	X	X	X	X	X	X	X	[X]	X	X	
Sub-study pracinostat/AZA PK sampling (ONLY IN SELECTED SITES) ^W			[X]	[X]	[X]							[X]			
Biomarker Analysis ^Z	X												X Even cycles	X	

SCHEDULE OF EVENTS (CONTINUED)

Assessments noted with [X] are to be done during Cycle 1 only. All other assessments are to be done during all cycles including Cycle 1, unless otherwise specified.

- A** Screening Visit should occur ≤ 28 days before commencement of Cycle 1 Day 1.
- B** There is ± 4 days window allowable between each clinic visit Day 1 Cycle.
- C** Written informed consent must be obtained prior to initiation of study related procedures
- D** Inclusion/exclusion criteria must be met prior to randomization. Patients <75 years of age must have at least 1 co-morbidity, per inclusion criterion 2. Eligibility criteria, including co-morbidities, must be reviewed by Medical Monitor prior to randomization.
- E** Bone marrow aspirate/biopsy samples will be collected and evaluated for:
 - **Morphologic evaluation:** at Screening (Section 6.1.1 of study protocol) to confirm AML diagnosis (local evaluation) and at the end of every even cycle, between Day 21 and Day 26, to evaluate the disease response to therapy at the Day 1 of each odd cycle (local evaluation). A morphologic evaluation of bone marrow already performed within 30 days prior to the ICF signature will be accepted as screening evaluation. Morphologic response assessment is required until a complete response is achieved and confirmed after 2 further cycles of treatment. At subsequent cycles, a bone marrow evaluation is no longer required, unless there is a suspicion of disease progression or relapse from CR. A bone marrow biopsy is only required in case of dry tap for the pathology interpretation of response, including bone marrow blasts.
 - **Classical cytogenetics** (karyotyping), with analysis of preferably 20 metaphases (central evaluation): at screening and at each subsequent bone marrow assessment, only if screening cytogenetic is abnormal, until the patient achieves a cytogenetic complete remission.
 - **MRD evaluation by MFC:** at screening and after 2 cycles from first CR
 - **Biobanking for mutational analysis** (mandatory in all patients)
 - If no bone marrow blood can be aspirated at screening (“dry tap”, even at repeated attempts) the patient will be considered a screen failurePeripheral blood and bone marrow fluorescence in situ hybridization (FISH) analysis for cytogenetic study and molecular analysis are not required. However if FISH testing or molecular analysis are part of the institution’s standard of care, the results will be recorded in the Case Report Forms.
- F** Smoking status will be collected at screening.
- G** Vital signs assessments will include: pulse rate, systolic and diastolic blood pressures (after the patient has been in the sitting or in semi-supine position for at least 5 minutes), body temperature, body weight.
Height will be only taken at screening.
Pulse rate, systolic and diastolic blood pressures will be measured:
 - (1) at screening
 - (2) pre-dose on Day 1 of Cycle 1 and Day 1 of Cycle 2
 - (3) at 90 minutes (± 30 minutes) post pracinostat/placebo administration on Day 1 of all Cycles and at Day 15 of Cycle 1
 - (4) at any time during the visit between Day 21 and Day 26 of Cycle 2
 - (5) at any time during EoT visitBody temperature will be measured:
 - (1) at screening
 - (2) on Day 1 of all Cycles (pre-dose)
 - (3) on Day 15 of Cycle 1 only

(4) at any time during EoT visit

Body weight will be measured:

- (1) at screening
- (2) on Day 1 all Cycles
- (3) at any time during EoT visit

H Complete physical examination will be performed at Screening. This evaluation will include an examination of general appearance, head, eyes, ears, nose, throat, skin, neck, lungs, cardiovascular, breast, lymph nodes, abdomen, musculoskeletal and neurological.

Limited physical examination, covering general appearance, cardiovascular, lungs and abdomen body systems, will be performed at Day 1 of each cycle to assess any changes that may have occurred since the last examination.

I ECOG performance status will be evaluated at screening and on Day 1 of each Cycle and EoT visit

J Information on transfusion of RBC or platelets (including date and type of transfusion) will be collected: at Day 1 of Cycle 1 (Section 5.1.2 of study protocol) and between Day 21 and Day 26 of Cycle 2 and all subsequent even cycles.

K Quality of Life Questionnaire to be administered on Day 1 Cycle 1 and on each Day 1 of odd Cycles and EoT visit.

L Triplicate 12-lead ECGs will be recorded (after the patient has been in sitting or in semi-supine position for at least 5 minutes):

- (1) at screening
- (2) on Day 1 of Cycle 1 (predose; at 90 minutes \pm 30minutes and 6 hours \pm 30minutes post pracinostat/placebo administration), on Day 2 of Cycle 1 (at 24 hours \pm 1hours post pracinostat/placebo administration), on Day 3 of Cycle 1 (at 48 hours \pm 1hours post pracinostat/placebo administration), on Day 15 of Cycle 1 (at 90 minutes \pm 30minutes post pracinostat/placebo administration),
- (3) on Day 1 of Cycle 2 (predose; at 90 minutes \pm 30minutes post pracinostat/placebo administration),
- (4) during the visit from Day 21 to Day 26 of Cycle 2 (any time)

Single 12-lead ECGs will be collected 90 \pm 30 minutes post pracinostat/placebo administration on Day 1 of each subsequent Odd cycle (i.e., Cycles 3, 5, 7, 9).

M Laboratory tests will be performed at a central laboratory. Samples for CBC, serum chemistry and coagulation are to be collected:

- (1) at screening within 8 days prior to Day1 of Cycle 1
- (2) at Day 15 of Cycle 1 only
- (3) at Day 1 of Cycle 2 only
- (4) between Day 21 and Day 26 starting from Cycle 2 and for all the subsequent Cycles
- (5) at any time during EoT visit

Hematology panel: complete blood count (CBC): hematocrit, hemoglobin, erythrocytes (RBC), platelets, leukocytes (WBC) with differential (neutrophils, lymphocytes, basophils, eosinophils, monocytes and blasts).

Blood chemistry panel: glucose, blood urea nitrogen/urea, creatinine, creatinine clearance (derived from blood creatinine value by Cockcroft formula), sodium, potassium, chloride, calcium, phosphorus, magnesium, bicarbonate/carbon dioxide (CO₂), alkaline phosphatase (ALP), alanine aminotransferase (ALT), aspartate aminotransferase (AST), totalbilirubin, total protein, uric acid, albumin, and lactic acid dehydrogenase (LDH).

Coagulation panel: PT, INR, PTT, fibrinogen, D dimer

Serum beta-hCG pregnancy tests: will be performed only of women childbearing potential at the Screening visit, on Day 1 of Cycle 2, between Day 21 and Day 26 of Cycle 2 and subsequent Cycles and EoT visit.

N HBV serology (HBsAg, antibody to HBsAg [anti-HBs], anti-HBc and HCV serology (anti-HCV) will be evaluated centrally only at screening. HIV will be performed based on local regulation at local laboratory at screening only. HIV test already performed within 30 days prior to the ICF signature will be accepted as screening evaluation.

-
- O** Urine dipstick pregnancy test will be performed locally at predose on Day 1 of Cycle 1 only for women of childbearing potential.
- P** Pracinostat Population Pharmacokinetic (PK) samples will be collected on Cycle 1: 30 minutes (± 15 minutes), 3 hours (± 30 minutes) and 6 hours (± 30 minutes); 24 hours (± 1 hour) before AZA administration; 48 hours (± 2 hours) before next pracinostat/placebo dose; Day 15 any time within 24 hours after pracinostat/placebo dosing for the day.
- Q** Pracinostat/placebo will be dispensed at the beginning of each cycle. The capsules are to be taken 3 times a week (e.g., Monday, Wednesday, and Friday) for 3 weeks, followed by 1 week of rest; this scheme will be repeated every 28-day cycle. Following Cycle 1, study medication compliance will also be assessed on Day 1 of each cycle. Pracinostat/Placebo oral administration is to be taken before SC or IV injection of AZA.
- R- S** The Investigator must ensure azacitidine administration information is collected for the study, including dose changes and administration route. AZA administration: 75 mg/m² via SC injection or as IV infusion on the first 7 days of every 28-day cycle. If unable to accommodate the Days 1-7 schedule, then the 5-2-2 schedule may be followed. Switch between Schedule 1 and Schedule 2 during the study period is acceptable.
- T** Pracinostat/placebo will be dispensed at Day 1 of each cycle and study drug compliance will be checked. At cycle 1, compliance will be checked on Day 15 as well.
- U** AEs and concomitant medications: assessed from the signature of ICF (concomitant medications from 21 days prior to Day 1 of Cycle 1) until 30 days from last study drug administration or until initiation of new AML treatment, whichever occurs first.
- V** In-study long-term Follow-up: After patients permanently discontinue study treatment, they will be followed every 3 months (± 1 month) from the date when study drug was last administered. Patients may be contacted during outpatient visits or by telephone. The following information will be obtained during these Follow-up contacts:
- Collect any new AML treatment
 - Collect any evidence of disease progression
 - Assess overall survival
 - When there is a suspicion of disease progression, a bone marrow evaluation is required to confirm disease progression
- W** **(IN SELECTED SITES ONLY)** Sub-study pracinostat/AZA Pharmacokinetic (PK) samples will be collected on Cycle 1: 15 minutes (± 2 minute), 30 minutes (± 2 minute), 1 hour (± 5 minutes), 2 hours (± 5 minutes), 3 hours (± 5 minutes), 4 hours (± 5 minutes), 6 hours (± 30 minutes), 8 hours (± 30 minutes) – optional sampling) after start of AZA administration; 24 hours (± 1 hour) before AZA administration; 48 hours (± 2 hours) before next pracinostat/placebo dose; Day 15 any time within 24 hours after pracinostat/placebo dosing for the day.
- Z** Biomarker Analysis (if consent obtained by patient): Peripheral blood samples and/or aspirate bone marrow samples will be collected and stored for potential molecular studies at screening and between day 21 and day 26 of every even cycle and at EoT visit (Section 6.4 of study protocol).

3.3 SAMPLE SIZE CONSIDERATIONS

This is an event-driven study. Sample size was computed for a group-sequential design with stopping rules for both futility and superiority (study-wise one-sided alpha level=0.025, power 0.90) with one interim analysis at 67% (2/3) of information and a final analysis. The alpha error spending function is from the O'Brien Fleming function for superiority and the Gamma family (with $\gamma=-5.4695$, more conservative than O'Brien Fleming) for futility (non-binding). Proportionality of hazards is assumed. Assuming that median OS is 10.0 months in the Group B (placebo + AZA) the aim is to detect, by means of the log-rank test or equivalent, an increase to 14.0 months in Group A (pracinostat + AZA), i.e. a HR of 0.714286. A total of 390 events (deaths) allows to meet a power requirement of at least 90% (actually 90.87%; it was 90% with the original function used in v1 protocol; further calculations kept fixed the number of events needed) at a study-wise one-sided significance level of 0.025.

4 ANALYSIS SETS

The following set definitions will be used in study summaries and analyses: All Randomized (ITT), ITT-2, Safety (SAF), Efficacy Evaluable 1 and 2 (EE-1 and EE-2), and Per Protocol (PP), and Pharmacokinetics (PK).

Data listings will present all the collected information per patient and will be based on all screened patients in the study.

4.1 ALL RANDOMIZED (INTENTION TO TREAT; ITT)

This set will comprise all randomized patients, regardless if the patient was administered study drug. Patients will be assigned to treatment groups based on the randomized study drug assignment. This set will be the primary set analyzed for the primary efficacy endpoint (OS) and the efficacy endpoint RFS, and will be also used for the analysis of durations of response (limited to patients with response), transfusion independence and for analysis of the efficacy endpoints CR rate, CR_{MRD}- rate and for the exploratory endpoints.

Summary tables of baseline and demographic data will be calculated for the All randomized set.

A specific ITT set is also defined: ITT-2. This set will comprise patients in the ITT set with abnormal cytogenetics at enrollment. This will be the primary set used for the analysis of the efficacy endpoint CRc rate.

4.2 SAFETY (SAF)

This set will comprise all patients who received at least one dose of pracinostat/placebo. Patients will be assigned to treatment groups based on the actual drug received. This set will be the primary set analyzed for safety and some baseline characteristics.

4.3 EFFICACY EVALUABLE (EE)

4.3.1 EE-1

The Efficacy Evaluable Set will include all patients in the ITT who had a complete disease response assessment. A complete disease response assessment was defined as at least 1 post-baseline peripheral blood count determined and 1 post-baseline bone marrow assessment performed, with an Investigator response reported. A peripheral blood count was defined as an assessment of absolute neutrophil count (ANC), platelets and peripheral blasts. In addition, patients who discontinued due to progressive disease per the Study Discontinuation form without a complete disease response assessment will also be included in this Efficacy Evaluable Set. This will be the secondary set used for the analysis of the efficacy endpoints CR rate, CR_{MRD}- rate and cCR rate.

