After patient has been re-evaluated, including review of laboratory parameters results, the Investigator will get connected to the IWRS for the assignment of a new study kit. The patient will be administered the same treatment assigned at Cycle 1 (active or placebo), but in case the dose reduction from 60mg to 45mg is considered to be necessary by the Investigator, this needs to be reported into IWRS according to dedicated section. The procedures to be completed are the same as for Cycle 1 (Day 1, Visit 2), except for randomization, i.e., for new cycle IWRS will only provide a new kit number for the patient according to the patient's randomization at Cycle 1.

5.1.9 Cycle 2 and All Subsequent Cycles on Days 2 to 7 (or 9)

- Pracinostat/placebo administration
- Review concomitant medications and therapies since the last study visit
- Assess AEs since the previous visit
- Administer azacitidine as detailed in Section 4.3.1.2 according to the chosen schedule (1-7 or 5-2-2)

The Investigator must ensure azacitidine administration information is collected for the study, including dose changes and administration route.

5.1.10 Cycle 2 and All Subsequent Cycles from Day 21 to 26

The last visit during Cycle 2 and following Cycles is to be scheduled within Day 21 and Day 26 (included) ensuring that the results of the performed analyses are available at the time of Day 1 of subsequent Cycles.

From Day 21 to 26 of each cycle, the following will be collected and/or performed (unless specified differently):

- 12-lead ECG measurement in triplicate at any time during the visit (**cycle 2 only**)
- Blood pressure and pulse rate (in sitting or in semi-supine position) to be measured at any time (**cycle 2 only**)
- Central laboratory assessments
- Serum pregnancy test for women of childbearing potential (Section 6.2.4)
- Assess AEs since the last study visit
- Review concomitant medications and concomitant therapies (including transfusions) since the last study visit

5.1.11 Cycle 2 and Subsequent Even Cycles from Day 21 to 26

- Response evaluation

Patients will be evaluated for disease response on Day 1 of each odd Cycle.

To assess response to therapy, a bone marrow aspirate/biopsy has to be performed between Day 21 and Day 26 of each **Even** Cycle (i.e., Cycles 2, 4, 6, 8 ...)

If the aspirate is a dry tap, then a bone marrow biopsy is required for the pathology interpretation of response, including bone marrow blasts.

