9.3 Analysis Sets

The definitions of analysis sets are as follows:

- 1) All randomized (Intent-to-Treat; ITT) - This set will comprise all randomized patients, regardless if the patient was administered study drug. Patients will be assigned to treatment groups based on the randomized study drug assignment. This set will be the primary set analyzed for the primary efficacy endpoint (OS) and will be also used for the efficacy endpoint RFS and the analysis of durations of response (limited to patients with response), transfusion independence, for the analysis of the efficacy endpoints CR rate , CR_{MRD}- rate and for the exploratory endpoints.
- 2) Safety - This set will comprise all patients who received at least one dose of study drug (pracinostat/placebo). Patients will be assigned to treatment groups based on the actual drug received. This set will be the primary set analyzed for safety.
- 3) Per Protocol (PP) – This set will comprise patients who met all eligibility criteria and received randomized study treatment without substantial deviations or violations. This set will be the secondary set analyzed for the efficacy endpoint OS.
- 4) ITT-2– This set will comprise patients in the ITT set with abnormal cytogenetics at enrollment. This will be the primary set used for the analysis of the efficacy endpoint CRc rate.
- 5) Efficacy Evaluable 1 (EE-1) – This set will comprise patients in the ITT set who had a complete disease response assessment. A complete disease response assessment is defined as at least 1 post-baseline peripheral blood count determined and 1 post-baseline bone marrow assessment performed, with an Investigator response reported. A peripheral blood count is defined as an assessment of absolute neutrophil count (ANC), platelets and peripheral blasts. In addition, patients who discontinued due to progressive disease (per the Study Discontinuation form) without a complete disease response assessment will also be included in this Efficacy Evaluable Set. This will be the secondary set used for the analysis of the efficacy endpoints CR rate, CR_{MRD}- rate and cCR rate.

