4.3.2 EE-2

The Efficacy Evaluable Set will include all patients in the ITT-2 who had a complete disease response assessment. A complete disease response assessment was defined as at least 1 post-baseline peripheral blood count determined and 1 post-baseline bone marrow assessment

performed, with an Investigator response reported. A peripheral blood count was defined as an assessment of absolute neutrophil count (ANC), platelets and peripheral blasts. In addition, patients who discontinued due to progressive disease per the Study Discontinuation form without a complete disease response assessment will also be included in this Efficacy Evaluable Set. This will be the secondary set used for the analysis of the efficacy endpoint CRc rate.

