7 STUDY POPULATION

7.1 PATIENT DISPOSITION

Patient disposition will be presented for all screened patients. The composition of the analysis sets and strata and those who were screened, failed screening, were randomized, treated, randomized and not treated, are still ongoing, discontinued from the study treatment, entered in long-term follow-up and those who discontinued from the long-term follow-up will be summarized by treatment group and overall. Reasons for discontinuation from study treatment will be presented with frequencies and percentages for all categories: adverse event, progressive disease, death, lost to follow-up, non-compliance by subject, physician decision, pregnancy, protocol deviation, withdrawal by patient, other. Reason for discontinuation will be also reported by cycle. Number of cycles performed by patients (by category or as median number) will be reported.

Also reasons for discontinuation from long-term follow-up will be presented with frequencies and percentages for all relevant categories (lost to follow-up, death, withdrawal by patient, physician decision, study terminated by sponsor, other).

Additionally, the number of patients where randomization code was broken by investigator together with the reason for breaking the code will be provided.

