8.2 SECONDARY ENDPOINT ANALYSES

The secondary efficacy outcome measures for this study are the following (the order is relevant to the sequence procedure for testing endpoints):

- Morphologic Complete Remission (CR) rate

- Transfusion independence
- CR_{M RD}- rate
- CR_c rate

A group-sequential procedure will be applied as described in section 5.5.

Morphologic Complete Remission (CR) rate

The rate of CR is defined as the proportion of patients who achieve a morphologic CR according to the IWG response criteria (Appendix F of the protocol) in the absence of interceding therapies, including salvage treatments and hematopoietic stem cell transplantation (HSCT), within the study period. Interceding therapies, salvage treatments, as well as HSCT are collected in the “New AML Treatment” eCRF page and in the concomitant medication page (if started before and continued into the treatment period or started during treatment period). The proportions in the two treatment groups will be compared using the Cochran-Mantel-Haenszel test stratified for cytogenetic risk and ECOG PS (values stated at randomization).

The level of significance to be adopted is described in Section 5.5.

In addition, the two-sided 95% CI for the difference between the responder proportions in the two treatment groups will be provided, using the stratified Newcombe method.

The analysis will be primarily performed in the ITT set (patients for whom no efficacy assessment is available will be analyzed as not having CR) and then in the EE-1 set.

Unstratified analysis will be done for sensitivity purpose by means of likelihood ratio Chi square test.

Logistic regression models will be set up including also demographic characteristics (especially the AML history variables as described in section 7.2) and factors described in section 5.3 as covariates to explore the influence of these variables on CR rate (likelihood ratio test to compare different models and Wald test to evaluate covariates within a model).

Transfusion Independence

For the evaluation of transfusion independence (which is defined as achieving eight weeks or longer with neither red blood cell nor platelet transfusions during the study period), the following transfusions are regarded as “relevant” transfusions:

- Red Blood Cell (RBC) transfusions
- Platelet (PLT) infusions
- Whole Blood infusions

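### EE-1 and EE-2 keep unassessed progressions but leave out unassessed deaths and adverse-event stops, so response rates are inflated in each arm and the comparison between arms is biased in an unknown direction

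*SAP*

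**What the plan says.** SAP 4.3.1 admits an ITT patient to EE-1 only with a complete response assessment, meaning "at least 1 post-baseline peripheral blood count determined and 1 post-baseline bone marrow assessment performed, with an Investigator response reported". SAP 4.3.2 applies the same rule to ITT-2 patients to form EE-2. Each definition then adds back one group of unassessed patients, those who discontinued for progression: "patients who discontinued due to progressive disease per the Study Discontinuation form without a complete disease response assessment will also be included". Protocol 9.3 has the same exception for both sets: "patients who discontinued due to progressive disease (per the Study Discontinuation form) without a complete disease response assessment will also be included".

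The role of EE-1 is stated as follows: "This will be the secondary set used for the analysis of the efficacy endpoints CR rate", and the sentence goes on to name CR-MRD- and cCR. For EE-2: "This will be the secondary set used for the analysis of the efficacy endpoint CRc rate".

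SAP 7.1 records death and adverse event as discontinuation reasons separate from progression: "adverse event, progressive disease, death, lost to follow-up, non-compliance by subject, physician decision". Neither is added back.

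On timing, Protocol 5.1.11 says "a bone marrow aspirate/biopsy has to be performed between Day 21 and Day 26 of each" even cycle, so the first scheduled post-baseline marrow falls in Cycle 2. The End of Treatment visit in Protocol 5.1.14 lists no marrow.

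For the primary CR analysis in ITT, SAP 8.2 says "patients for whom no efficacy assessment is available will be analyzed as not having CR".

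**The concern.** The add-back accepts that a treatment failure belongs in the denominator even without a marrow, but applies this to one kind of failure only. Take two patients who leave treatment in week five with no marrow. One is recorded as progression and stays in EE; the other is recorded as death or adverse event and drops out. Inclusion then depends on an outcome after randomization and on the reason entered on a form.

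A CR under Protocol Appendix F needs marrow and blood counts, so the dropped patients contribute no responders. Taking them out shrinks the denominator and leaves the numerator alone. At stake is the second planned reading of CR, CR-MRD-, cCR and CRc. If the arms differ in early death or early toxicity, the EE comparison mixes that difference with the effect on response, and EE agreement or disagreement with ITT becomes hard to interpret.

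The exclusion is limited. A patient with one complete assessment before dying or stopping remains in the set.

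**Working it through.** **Inputs.** CR 0.20 on placebo, with an assumed difference of 0.13, hence 0.33 on pracinostat (SAP 5.5). One-sided level 0.025 (SAP 5.5). 500 patients, 1:1, so 250 per arm (Protocol 9.11, SAP 5.2). Median OS 10.0 and 14.0 months (SAP 3.3). A month is 30.4375 days (SAP 6.4).

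**Reproducing the plan's figure.** SAP Table 2 gives 0.91 as the probability of a significant CR result taken as the only endpoint. The pooled rate is 0.265. The standard error is √(0.265 × 0.735 × 2/250) = 0.0395 under the null and √((0.20 × 0.80 + 0.33 × 0.67)/250) = 0.0390 under the alternative. Power = Φ((0.13 − 1.96 × 0.0395)/0.0390) = 0.911, which agrees.

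**Time to first scheduled marrow.** Cycle 2 Day 21 is study day 28 + 21 = 49, or 49/30.4375 = 1.610 months.

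**Deaths before day 49**, assuming exponential survival from randomization:
- placebo: 1 − exp(−ln 2 × 1.610/10) = 10.6%
- pracinostat: 1 − exp(−ln 2 × 1.610/14) = 7.7%

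**Effect on EE.** Every excluded patient is a non-responder in ITT, so EE rate = ITT rate/(1 − share excluded). Deaths alone give 0.20/0.894 = 22.4% and 0.33/0.923 = 35.7%.

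The documents give no exclusion shares by arm. Every row of the table below the deaths-only row is an assumption, and the rows cover both directions of imbalance.

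| Excluded, placebo/pracinostat | EE CR, placebo | EE CR, pracinostat | Difference (points) | Ratio |
|---|---|---|---|---|
| none (ITT) | 20.0% | 33.0% | 13.0 | 1.65 |
| 10.6/7.7% (deaths only) | 22.4% | 35.7% | 13.4 | 1.60 |
| 10/10% | 22.2% | 36.7% | 14.4 | 1.65 |
| 10/20% | 22.2% | 41.3% | 19.0 | 1.86 |
| 20/10% | 25.0% | 36.7% | 11.7 | 1.47 |

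**No true effect (20% in both arms).**
- 10/10%: difference 0
- 10/20%: 25.0% − 22.2% = +2.8 points
- 20/10%: 22.2% − 25.0% = −2.8 points

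With 250 randomized per arm, the nominal one-sided error favouring pracinostat is then about 0.025, 0.10 and 0.004 respectively.

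**Where the direction turns.** The ratio is unchanged when both arms lose the same share, and it falls as soon as placebo loses more. The difference stays above 13.0 points until placebo losses are clearly larger. If pracinostat loses 10%, its EE rate is 36.7%, and the difference equals 13.0 when placebo's EE rate is 23.7%. That is a placebo loss of 1 − 0.20/0.237 = 15.5%.

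**The case against.** A reader might infer that the EE sets overstate the benefit of pracinostat, on the argument that an added drug brings added toxicity and so more exclusions in its arm. The documents do not support that step. They give no early-exclusion rate by arm. Their own survival assumption puts more early deaths on placebo, which leaves the difference almost unchanged and lowers the ratio. On toxicity they point both ways. Protocol 3.3.3 calls the safety profiles similar and suggests that the combination is no more toxic. Protocol 4.5 attributes severe fatigue, vomiting, diarrhea and other reactions to pracinostat, and Protocol 1.3 reports two Phase II deaths considered related to both drugs. The survival-based figure does not settle direction either: it assumes constant hazards, and SAP 8.1.2 itself reports that proportional hazards evidently fail for treatment.

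Four further points on the other side:

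- **ITT is primary.** CR, CR-MRD- and cCR are analysed first in ITT with unassessed patients as failures (sites unable to assess MRD apart), and CRc in ITT-2. The SAP 13 table labels the EE rows as secondary or sensitivity. This stands and is why the point is minor.
- **Imbalance will partly show.** SAP 7.1 reports set composition by arm and discontinuation reasons by arm and cycle, and SAP 9.2.5 reports deaths within 30, 60 and 90 days. This stands in part, because no planned table links EE exclusion to its reason.
- **An adverse-event stop without a marrow is not a documented failure, whereas progression is.** This is fair for toxicity stops and weaker for deaths. The ITT rule nevertheless counts both as non-responders.
- **Some patients will have an earlier marrow.** Protocol 4.5.1 suggests one at day 42 if counts have not recovered. This narrows the excluded group without removing it.

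**Conclusion.** The asymmetry is in the current text of both documents and affects both EE sets. It inflates the response rate in each arm wherever unassessed deaths or adverse-event stops occur. The bias between arms has unknown direction. The only case built from the plan's figures moves the CR difference from 13.0 to 13.4 points and the ratio from 1.65 to 1.60. Assumed losses of 10% to 20% per arm put the difference anywhere from 11.7 to 19.0 points and, with no true effect, from −2.8 to +2.8 points.

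These sizes rest on exponential survival for the deaths-only case and on assumed shares otherwise. The arithmetic is for CR; the same mechanism applies to CR-MRD-, cCR and CRc, for which the plan gives no assumed rates. No confirmatory conclusion is at risk, because the EE analyses carry no alpha. Severity is minor: a supportive analysis whose bias cannot be signed adds little support, and it is cheap to repair.

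**What to change.** In SAP 4.3.1 and 4.3.2, and in both EE definitions in Protocol 9.3, replace the add-back with: *Patients who died, or who stopped study treatment because of an adverse event or progressive disease, and who have no complete disease response assessment, are included and counted as non-responders.* Add a table of the remaining EE exclusions by arm and reason.

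The cost is one sentence per set and one table, using disposition and death data already collected. EE moves closer to ITT and its response rates become slightly lower. It stays a distinct set, because withdrawals, losses to follow-up and other missing marrows remain outside it.
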